## Figure 1: Trial Design (VectivBio AG 2023)

aGVHD=acute graft versus host disease; CR=complete response; D=Day; GI=gastrointestinal; iSRC=Independent Safety Review Committee; R=randomization

1. Review of the first six subjects randomized to two treatment arms
2. Exact dose depends on the weight of a subject a baseline (randomization/Day 0).
3. Apraglutide will be administered weekly for 8 weeks (Week 0 to Week 7). Treatment can be continued up to 13 weeks (Week 8 to Week 12) if a CR is not achieved at Week 8.

If there is no CR at Week 13 optional treatment is allowed for a maximum of 13 weeks (Week 13 to Week 25, inclusive) or until a complete lower GI-aGVHD response is achieved, whichever comes first. Optional treatment can only be started if additional apraglutide treatment would benefit the subject based on the Investigator's assessment. Treatment can be re-started in case of a lower GI-aGVHD flare during follow-up (between Week 9 and Week 25) at the same dose given at randomization/Day 0 providing that apraglutide treatment was previously stopped if a lower GI-aGVHD CR was achieved at Day 56 (or a PR or CR was achieved at Day 91. Only one re-treatment course is allowed and should not last more than 13 weeks

## 2.2 Randomization

Subjects weighing more than 50.0 kg are randomly assigned to low dose or high dose in a 1:1 ratio following a block randomization scheme described in the “Randomization and Study Product Management Requirement Specifications”, V6.1, Section 16: Randomization Plan.

## 2.3 Sample Size Determination

The sample size calculation was fully reported in the protocol (section 7.8.1). It was planned to randomize 30 subjects to the 2 trial arms on a 1:1 ratio. It is calibrated such as five out of seven responders at the interim analysis enable a detection of an apaglutide signal at least 10% greater than the historical reference Day 56 durable overall response rate on the Lower GI MAGIC score with a probability of 88.2%.

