	
methods comparing the observed results in each treatment arm with a historical control dataset.
 
Analysis
 
An interim analysis will be performed when 17 subjects have either reached Day 56 or withdrawn from the trial. All available data points by the data cut-off date will be included in the analysis.
 
The final analysis will be done in two steps. The primary analysis of safety and efficacy will be performed once all subjects have either completed Day 91 or withdrawn from the trial. Additional analyses will be done once all the subjects have either completed the EOT visit or withdrawn from the trial. A Clinical Trial Report (CTR) will be issued after the primary analysis. An addendum to the CTR will cover the follow-up period until 2 years after the first apaglutide dose.
 
Sample Size
 
Up to 34 subjects with SR lower GI-aGVHD who are taking BAT will be randomized in this trial. The sample size justification was based on a selected secondary endpoint (Day 56 GI response). Observed response rates of 5/7 (71%) subjects at the interim analyses will lead to a high probability (>88%) of effectiveness comparing apaglutide and BAT with a historical Day 56 response rate derived from the previous trial, REACH2, including a 10% penalty.
 
Analysis Sets
 
The Full Analysis Set (FAS) comprises all enrolled subjects (randomized and non-randomized LBWs). All efficacy evaluations will be conducted using the FAS according to the planned dose (high dose, low dose, LBW dose) and in total.
 
The LBW Analysis Set comprises all subjects with a body weight ranging from 40.0 to <50.0 kg assigned to receive 2.5 mg apaglutide who actually received at least one dose of therapy and who have provided at least one post-baseline assessment for any endpoint. All endpoints will be analyzed for this set separately.
 
Safety Analysis Set 1 (SAS1) comprises all randomized subjects exposed to either of the two randomized apaglutide dose levels. All principal safety analyses will be carried out on the SAS1 according to the dose of apaglutide received.
 
Safety Analysis Set 2 (SAS2) comprises all randomized and non-randomized subjects exposed to any apaglutide

--	---

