7.4 Determination of Sample Size

The principal statistical goal of this trial from an efficacy perspective is to estimate the likelihood of efficacy of apaglutide therapy in the treatment of subjects with SR lower GI-aGVHD after alloSCT. Published, randomized control trial data on BAT in the treatment of such subjects [Zeiser, 2020a] provides estimates of overall response rate at Day 28 of 62% (96/154) and durable overall response at Day 56 of 40% (61/154). Further, the GI-aGVHD response rate at Day 28 of 57% (55/96) is also published [Zeiser, 2020b]. At the time of trial initiation, this was considered the best matched information available for a reasonable sample size determination.

Assuming same degree of decline of GI response from Day 28 to Day 56 as observed for an overall response from Day 28 to Day 56, the GI response at Day 56 can be estimated as 36% (r=35 responses in n=96 subjects). These data provide a reliable prior for the true response rate on BAT, π_r , such that $\pi_r \sim \text{Beta}(r+1, n-r+1) = \text{Beta}(36, 62)$.

In the current trial, it is planned to randomize 30 subjects on a 1:1 basis to high or low dose apaglutide. Assuming a non-informative prior for the Day 56 GI response rate with apaglutide, 15 subjects per dose will provide a posterior distribution for the true response rate with apaglutide π_a , such that $\pi_a \sim \text{Beta}(s+1, 15-s+1)$ where s is the observed number of successes on any given dose. Using the prior for BAT response, π_r , and the posterior for the apaglutide response, π_a , it is possible to construct the posterior distribution for the true difference in response rates, $\pi_a - \pi_r$.

Considering a penalty on the original assumptions that are based on Day 56 durable overall response instead of Day 56 response, one can still detect an effect of apaglutide over BAT.

At least five out of seven responders at the interim analysis will be able to detect a signal of apaglutide at least 10% greater than the Day 56 durable overall response with a probability of 88.2%.

In case of a sufficiently large response rate in a single treatment arm, the planned sample size will allow for reliable conclusions regarding the effectiveness of apaglutide relative to BAT for Day 56 response rate in the treatment of subjects with SR lower GI-aGVHD after alloSCT. Considering a penalty on the original assumptions, we can still detect an effect of apaglutide over BAT.

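### SAP 2.3 presents 88.2% as a detection probability that calibrates the 30-subject plan; it is a posterior probability given 5/7 already observed at the interim, and neither 15 nor 30 enters it

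*SAP*

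**What the plan says.** **SAP 2.3** gives the plan of 30 subjects randomized 1:1 and continues: "It is calibrated such as five out of seven responders at the interim analysis enable a detection" of a signal at least 10% above a historical durable Day 56 lower GI rate, with probability 88.2%. For the derivation it says: "The sample size calculation was fully reported in the protocol (section 7.8.1".

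**Protocol 7.4** holds the calculation.
- It quotes from the earlier randomized trial a "durable overall response at Day 56 of 40% (61/154", and derives a Day 56 GI rate on BAT of 36% (35/96), hence Beta(36,62).
- It sets up a flat-prior posterior for 15 subjects per dose.
- It then writes "Considering a penalty on the original assumptions that are based on Day 56 durable overall response instead of Day 56 response", followed by "At least five out of seven responders at the interim analysis will be able to detect a signal of apaglutide" and "at least 10% greater than the Day 56 durable overall response with a probability of 88.2" percent.
- It concludes that, if the response rate in one arm is large enough, "the planned sample size will allow for reliable conclusions regarding the effectiveness of apaglutide relative to BAT".

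**The protocol synopsis** words the same result differently: "Observed response rates of 5/7 (71%) subjects at the interim analyses will lead to a high probability (>88%) of effectiveness", against a Day 56 rate derived from the earlier trial with a 10% penalty.

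**SAP 4.3.9.2** plans the Day 56 lower GI analysis as a proportion with a two-sided 95% Clopper-Pearson interval. **SAP section 6** places the sample-size reference on the lower GI score (item 3) and says that the comparison with external BAT data is not planned for the Primary Analysis (item 7).

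**The concern.** Placed directly after the 30-subject plan, with the words *calibrated* and *detection*, 88.2% reads like power: the chance that a trial of this size finds an effect. A reader of the SAP, and later of the clinical trial report (CTR), could carry it forward as an operating characteristic of N=30. If it is instead a statement about one favourable interim result in seven subjects, the sizing section states a design property that the trial does not have. It also leaves out the property that 15 per arm and 30 combined do deliver under the planned analysis, namely interval width. And once the BAT comparison is dropped from the Primary Analysis, Protocol 7.4's promise of reliable conclusions relative to BAT has no planned analysis behind it at that step.

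**Working it through.** **Inputs**
- Observed data 5/7 (synopsis, Protocol 7.4). With the flat prior of Protocol 7.4, the posterior is Beta(s+1, n-s+1) = Beta(6,3).
- Historical GI rate at Day 56: 55 Day 28 responders × 61/96 = 34.9, so 35/96 = 36.5%, giving Beta(36,62) (Protocol 7.4).
- Margin or penalty: 10%, read as 10 percentage points.

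**Step 1: reproduce the stated figure.** The quantity is P(π_a > π_r + 0.10), the integral over x of the Beta(36,62) density times P(Beta(6,3) > x + 0.10). Numerical integration gives 0.8857, or 88.6% against the stated 88.2%. As a rough check, fix the reference at 0.4646: P(Beta(6,3) > 0.4646) = 0.8971. Allowing for uncertainty in the historical rate lowers this to 0.8857.

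**Step 2: other readings of the reference, all given 5/7**

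| Reference | Posterior probability |
|---|---|
| 35/96 plus 10 points | 88.6% |
| Penalty added to the historical count: 35 + 9.6 = 44.6, rounded to 45/96, no further margin | 88.3% |
| 61/154 plus 10 points (Protocol 7.4 taken literally), Beta(62,94) | 85.3% |
| 35/96 raised by a relative 10% | 93.9% |

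**Step 3: which sample size enters.** For integer parameters P(Beta(6,3) > x) = P(Bin(8, x) ≤ 5), where 8 is 7 + 1. At x = 0.50 this is 1 − 37/256 = 0.8555. Only n = 7 appears. Protocol 7.4 writes the model for 15 per dose but attaches no probability to 15 or to 30. For illustration only, and not as a success rule, the same posterior against 35/96 plus 10 points is 82.7% at 9/15, 92.1% at 10/15, 83.0% at 17/30 and 89.8% at 18/30.

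**Step 4: is it a detection probability?** The chance of observing at least 5 of 7 is a binomial tail that depends on the true rate. The documents assume no true rate for apraglutide, so a range is shown.

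| Assumed true rate | P(at least 5 of 7) |
|---|---|
| 50% | 22.7% |
| 60% | 42.0% |
| 70% | 64.7% |
| 80% | 85.2% |

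The tail reaches 88.2% only at a true rate of 81.8%, which no document states.

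**Step 5: what the planned analysis delivers.** The exact 95% Clopper-Pearson interval at an observed 60% is:
- 9/15: 32.3% to 83.7%, about 51 points wide;
- 18/30: 40.6% to 77.3%, about 37 points wide.

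**Step 6: cross-reference.** Protocol 7.8.1 describes the Day 56 analysis and mentions that the endpoint was used for sizing. It contains neither 5/7 nor 88.2%; both are in 7.4.

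**The case against.** The best defence is that the documents already guard against the misreading. The synopsis words the figure correctly, as conditional on an observed 5/7. Protocol 7.4 sets out the posterior model just before the number. Protocol 7.1 and 7.2 say that the aim is estimation and that the interim involves no hypothesis test or alpha spend. The primary objective is safety, and no decision rule uses 88.2%. All of this stands, and it limits the consequence. It does not rescue SAP 2.3, which ties the number to the 30-subject plan and sends the reader to a section where the model for 88.2% cannot be checked.

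A reader might also draw three stronger conclusions, which the documents do not support.

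- *That 88.2% is an arithmetic error, or that its reference cannot be identified.* The synopsis, SAP 2.3 and SAP section 6 item 3 point to the derived lower GI rate, and 35/96 plus 10 points comes within half a point. Nor is 45/96 the only model that fits. The number of draws behind 88.2% is not stated. At 10,000 draws the standard error is √(0.8857 × 0.1143 / 10,000) = 0.0032, so the gap of 0.0037 is little more than one standard error. The 100,000 draws in Protocol 7.8.1 are specified for the final analysis.
- *That the 7 contradicts the interim at 17.* Seventeen subjects split 1:1 are 8 or 9 per arm. Seven per arm would fit if some of the 17 were low-body-weight subjects, and the interim SAP (v1.0) is not among the documents. This is a request for clarification, as is the shift between penalty and margin wording: adding 10 points to the reference and requiring a difference above 10 points are the same calculation.
- *That the loss of the BAT comparison is undisclosed.* SAP section 6 item 7 discloses it; SAP 2.3 merely does not point there.

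**Conclusion.** The point holds as one of labelling and placement. The 88.2% in SAP 2.3 and Protocol 7.4 is a posterior probability given 5/7 at the interim, about 88% against 35/96 plus 10 points. It is not a probability of detection, and it does not calibrate N=30. Protocol 7.4's literal reference, 61/154, gives 85.3%, about 3 points lower, so that wording needs aligning with the lower GI reference. The SAP's cross-reference is wrong. Protocol 7.4's claim about conclusions relative to BAT has no planned analysis at the Primary Analysis.

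This rests on the documents' flat prior and on reading the 10% as percentage points; the true rates in Step 4 are assumed. Nothing here shows that 30 is the wrong number for a proof-of-concept trial with a safety primary objective. The correction is worth making because the CTR could otherwise repeat 88.2% as a property of the design.

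**What to change.** **In SAP 2.3:**
1. Drop *calibrated* and *detection*. Suggested text: *If 5 of 7 subjects respond at the interim, the posterior probability that the apraglutide Day 56 lower GI response rate exceeds the historical lower GI reference (35/96) by more than 10 percentage points is about 88%. This is not a property of the 30-subject design.* The sponsor should confirm the model actually used and say how the 7 relates to the 17.
2. Give the precision of the planned analysis, for example the Clopper-Pearson intervals at 9/15 and 18/30 shown above.
3. Correct the cross-reference from Protocol 7.8.1 to 7.4.
4. Point to section 6 item 7 and state that the BAT comparison behind the figure is not performed at the Primary Analysis.

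**For Protocol 7.4:** align the durable-overall-response wording with the lower GI reference, and qualify the sentence on conclusions relative to BAT. A note in the SAP and in the CTR, where Protocol 7.9 already requires deviations to be reported, is enough.

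**Cost:** one rewritten paragraph and a short note. N, data and planned analyses are untouched; SAP v2.0 (1 February 2024) postdates the 1 December 2023 cut-off in any case. The downside is that the stated property becomes less favourable and the wide intervals become visible.

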# 3 TRIAL ENDPOINTS

## 3.1 Safety endpoints

- Adverse events (AEs; System Organ Class [SOC], frequency, and severity)
- Incidence of AEs of special interest (AESIs):
  - Injection site reactions
  - Gastrointestinal obstructions
  - Gallbladder, biliary, and pancreatic disease
  - Fluid overload
  - Colorectal polyps
  - Newly diagnosed malignancies
  - Systemic hypersensitivity
- Occurrence of clinically significant changes from baseline in:
  - Clinical chemistry (including liver function tests), hematology, hemostasis, and urinalysis
  - vital signs (blood pressure, heart rate)
  - electrocardiogram (ECG) measurements (intervals and rhythm)
- Occurrence and titer of anti-drug antibodies (ADAs)
- Physical Examination

### 3.2 Secondary endpoints:

- Overall response rate at Day 56 on the lower GI tract MAGIC stage: defined as proportion of subjects with complete response (CR) or partial response (PR) on the lower GI tract MAGIC stage at Day 56.
- Overall response rate (PR and CR) at Days 14, 28, 91, 119, 147, and 182 on the lower GI tract MAGIC stage.
- Overall response rate (PR and CR) at Days 14, 28, 56, 91, 119, 147, and 182 by organ system (skin, lower and upper GI tract, and liver) on the total MAGIC grade.
- Proportion of all subjects who achieve a CR or PR at Day 28 and maintain a CR or PR at Day 56 [Only for Primary Analysis].
- Individual duration of lower GI response (according to the MAGIC score)
  - counted from the first response to return to baseline or worse
  - in subjects that were re-treated with apaglutide because of a lower GI-aGVHD flare, counted from the first response after apaglutide restart to return to baseline or worse
- Time to:
  - Partial lower GI-aGVHD response as defined by the MAGIC score
  - Complete lower GI-aGVHD response as defined by the MAGIC score
- Duration of response from Day 56 on the total MAGIC score: defined as the interval from the Day 56 response (PR and CR) to death or new systemic therapy for aGVHD (including an increase in steroids >2 mg/kg/day methylprednisolone (MP) equivalent), whichever occurs first, with at least 182 days of follow-up
- Duration of response from Day 28 on the total MAGIC: defined as the interval from the Day 28 response (PR and CR) to death or new systemic therapy for aGVHD (including an increase in steroids >2 mg/kg/day MP equivalent), whichever occurs first, with at least 182 days of follow-up
- Best overall response defined as overall response (PR or CR) at any time point up to and including Day 91 and before the start of additional systemic therapy for lower GI-aGVHD [Only for Primary Analysis]
- Failure-free survival up to 2 years post-first dose of apaglutide
- Incidence of malignancy relapse up to 2 years post-first dose of apaglutide [Only for EOT Analysis]
- Non-relapse mortality up to 2 years post-first dose of apaglutide

- Overall survival up to 2 years post-first dose of apaglutide [Only for EOT Analysis]
- Incidence of lower GI-aGVHD flare up to Day 182 after the first apaglutide dose following earlier cessation due to complete lower GI-aGVHD response
- Incidence of graft failure up to 2 years post-first dose of apaglutide [Only for EOT Analysis]
- Cumulative SS and RUX doses from start of the RUX treatment up to Day 91 after the first dose of apaglutide [Only for Primary Analysis]
- Incidence of infections and sepsis from baseline to Day 91 and overall after the first dose of apaglutide

